9.1 Study Design – General Aspects

The effectiveness objectives will be addressed through a retrospective cohort study using linked secondary databases in England accessed through ORCHID and NHS Digital's TRE. Persons vaccinated with Oxford/AstraZeneca COVID-19 vaccine or another COVID-19 vaccine will be compared to matched persons not vaccinated with any COVID-19 vaccine for occurrence of study outcomes.

Due to England's vaccination campaign starting with the older age group, as of March 22 2021, over 90% of people 70 years of age or older were vaccinated with at least one dose of any COVID-19 vaccine (Public Health England, 2021). Therefore, it is expected that the concurrent control arm will have considerable challenges. A greater proportion of younger people might be included who may have lower hospitalization and death (particularly because the Joint Committee of Vaccination and Immunisation (JCVI) recommended early vaccination of people 16 to 64 years with comorbidities). Additionally, people receiving terminal care and those who do not engage much with the health system may also be included. For these reasons, the concurrent control arm is matched with the vaccine arm by age and other characteristics. Events' rates will also be stratified by age groups (e.g. 12-15,16-49, 50-64, 65-69, 70-79, 80+).

We will also explore how COVID-19 vaccination in England coincided with the 3rd wave of COVID-19 and any subsequent wave that may occur. For this analysis, we will include vaccination data periods beyond February 2021.

There have been changes in the age groups vaccinated and the introduction of booster doses. The Moderna and Pfizer BioNTech vaccines have been licenced for children (Medicines and Healthcare products Regulatory Agency (a & b), 2021) and booster doses were introduced in the autumn of 2021. For these reasons the analyses will be extended to include the 12–16-year-old age-group and any booster vaccination (9)(Department of Health and Social Care, 2021). Finally, the UK COG has centralised data on COVID-19 variants allowing VE to reported by variant.

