9.2.2 Inclusion Criteria

The study population is required to meet the following inclusion criteria:

1. For the vaccinated arms:

- Any COVID-19 vaccination at the index date
- Have continuous data coverage for the COVID-19 infection datasets, i.e. Second Generation Surveillance System (SGSS) and National Pathology Exchange (NPEX) from their initiation for history of prior COVID-19 infection
- Have continuous data coverage in other linked databases for a minimum of 12 months prior to the index date for assessment of baseline variables including socio-economic status, comorbidities, and follow-up of outcome events.

2. For the control arms:

- Eligible for any COVID-19 vaccination based on age at the index date for the concurrent control individuals.
- Have continuous data coverage for the COVID-19 infection datasets, i.e. SGSS and NPEX from their initiation for history of prior COVID-19 infection
- Have continuous data coverage in other linked databases for a minimum of 12 months prior to the index date for assessment of baseline variables including socio-economic status, comorbidities, and follow-up of outcome events.
- People who have not (yet) received any COVID-19 vaccine (Oxford/AstraZeneca, Pfizer, or Moderna COVID-19 vaccine) recorded in their GP record or in NIMS. They will be used as concurrent controls. However, they will be censored at date of vaccination and, then may re-enter the study as newly vaccinated individuals.

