9.3.3 Other Variables and Covariates

Table 6. Variable categories and data sources

Variables	Categories	Data source	Comment
Age	Different categorizations may be used -12 <50; 50-<65; 65-<70; 70-<80; 80+ -18-<40; 40-<50; 50+; 65+; 70+; 80+	GDPPR	BMI is binary as obese or not using HES, SUS, GDPPR or BMI can be created from weight/height if
Gender	Male/Female	-	available;
Ethnicity	White, Black, Asian, Other, Mixed		
Region	NHS Region	-	
Sociodemographic	Socioeconomic status – Index of Multiple Deprivation (IMD)		
BMI	-Obese (BMI 30+) -Not-obese (BMI <30)		
Smoking	- Current - Past - Non smoker		
Comorbidity	Specific comorbidities known to relate with increased risk of severe COVID- 19 and/or suboptimal vaccine response and/or vaccine contraindication including chronic respiratory disease, chronic kidney disease, chronic heart disease and vascular disease, chronic liver disease, chronic neurological disease, diabetes mellitus, severe mental illness, morbid obesity, asplenia or dysfunction of the spleen, and immunosuppression due to disease or treatment.	ORCIHD, HES and GDPPR	Follow JCVI/Green book list of comorbidities (COVID-19 Greenbook chapter 14a) Using ICD or SNOMED codes to identify comorbidities during the baseline period. For immunosuppressant medications, see Prescribed medication section below.
CMMS	0, and by quartile		Created from specific comorbidities;
Non-COVID-19 vaccination	 Flu vaccination (Y/N) Receive adequate vaccination (Y/N) 	GDPPR	An algorithm will be developed to determine if an individual is adequately vaccinated according to recommended vaccination schedule by age and comorbidity status
Prescription medication	Immunosuppressant vs. not	GDPPR	Prescribed medications at baseline will be grouped into immunosuppressant or not.
LTC /assisted living care facility	Yes/No	Not in any database	To be created for people aged 70+ by comparing their zip codes and LTC

Variables	Categories	Data	Comment
		source	
			address; or vaccination at LTC facility. (ORCHID)
Household composition	Size and age combination.	ORCHID UKHSA VE cohort	Available for 7.2 million subset of ORCHID
Frailty score	eFI grouped into - Mild - Moderate - Severe	Derived from GDPPR	Use an algorithm already developed to derive eFI, only available for population 65years and older. For this sub-group analysis.

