9.7 Data Analysis

9.7.1 Statistical Methods – General Aspects

A detailed SAP will be developed for this analysis. The SAP may modify the plans outlined in the protocol; any major modifications of primary endpoint definitions or their analyses would be reflected in a protocol amendment. For all study designs, p-values will be quoted to two decimal places, unless they are less than 0.001 (whereby the p-value will be given as < 0.001) or between < 0.005 and > 0.001, in which case they will be stated to three decimal places. Parameter estimates will be reported with 95% CIs. All statistical tests are 2 sided and with a 5% significance level.

A CONSORT 2010 Flow Diagram of the study population detailing each step of the inclusion and exclusion criteria applied will be generated. As indicated in section 9.4, to obtain the most followup data, the primary analysis will include all HES data until 8 weeks prior and all raw hospitalization data (SUS) from 8 weeks to 2 weeks prior database lock. A sensitivity analysis including only HES data, therefore a shorter follow-up for hospitalization, will also be done.

For the concurrent control arm, each week starting from 8th December 2020, we will match all newly vaccinated persons in a 1:1 ratio to unvaccinated controls (Dagan et al, 2021). Newly vaccinated persons will be eligible for inclusion in the study, even if they will have previously been selected as a control. We will match vaccine recipients and controls on variables associated with the probability of both vaccination and infection or severity of COVID-19: age (study defined age bands), gender, general practice, (or NHS Region), and comorbidity as defined by CMMS quartile. We will exact match each week (if feasible). To assess the quality of matching, love plots will be created showing the mean standardized difference between each vaccinated cohort (AstraZeneca or other vaccine cohort) and the comparator cohorts in participants' characteristics. If important differences are observed, the matching criteria will be refined.

The demographic and characteristics of study participants in each vaccine arm and its respective control arm at baseline will be determined during the 12-month period before index date using the measurement closest to index date.

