Summary tables of all patient characteristics and end points indicated in section 9.3.2 will be created for both the before and after matching situation to provide insight in population characteristics as well as in errors and missingness. Categorical variables will be checked on meaningful categories and frequencies. It is not anticipated that categories will have too low frequency. Pooling will be considered when the frequency for a category becomes below 1000.

Continuous variables will be summarized in terms of min, max, interquartile range, median and mean to get insight in these variables, but also to provide a first indication of use of same unit across the database and to obtain a first impression about possible transformations needed. Missing values will be considered in detail. If the percentage of missingness is below 10%, complete case analyses will be performed. When exceeding 10%, multiple imputation will be run additionally based on the total dataset.

For each outcome event, the summary tables will present for each study cohort the number of first events, total person-years for the event and number of first events per person-years (rate), the RR and the VE which is calculated as 1 - RR. This will also be provided per age group and per frailty score where further stratification/subgroups are indicated below. Finally, VE will also be provided in shorter periods after dose 1, and between the doses, and presence of comorbidities.

Poisson regression with offset for time at risk will be used to estimate rates using the matched dataset, adjusting for the matching variables and BMI, smoking, prescribed medications, and frailty score, which are known to increase risk of hospitalization and death and are likely associated with vaccination.

Checks on linearity for continuous variables will be performed. In order to evaluate interactions of independent variables with the exposure (i.e. vaccinated/comparator), continuous variables will be categorized and the VE will be tabulated per category. For variables for which the maximum and minimum VE across categories is more than 10% different, interaction effects with the exposure will be taken into account in the Poisson model. For interactions among independent variables that are not the exposure, interaction variables will be created. Forward selection is performed, and interaction variables will be included when the computed VE changes with more than 10%.

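### A 12-month look-back counts older chronic diagnoses as absent, misclassifying the comorbidity score used for matching and leaving avoidable confounding of uncertain sign

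*Protocol*

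**What the plan says.** Section 9.7.1 states that the characteristics of each vaccine arm and its control arm "at baseline will be determined during the 12-month period before index date using the measurement closest to index date". Table 6 in section 9.3.3 describes how comorbidities are found: "Using ICD or SNOMED codes to identify comorbidities during the baseline period". The same table says of the CMMS that it is "Created from specific comorbidities". No other place in the protocol gives the baseline period a length.

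The comorbidity information is then used in three places:
- Matching: section 9.7.1 matches on "comorbidity as defined by CMMS quartile".
- Outcome model: the Poisson regression is fitted "adjusting for the matching variables and BMI, smoking, prescribed medications, and frailty score".
- Stratification: comorbidity status is one of the breakdowns of the primary objective (section 8, Table 3).

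Section 9.2.2 asks for "continuous data coverage in other linked databases for a minimum of 12 months prior to the index date". That is a minimum: it would allow a longer look-back but does not provide one.

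**The concern.** Table 6 lists conditions that persist once diagnosed, such as asplenia, diabetes and chronic kidney, liver, heart or neurological disease. Such a condition may have been coded years ago and not again in the last 12 months. Under the rule as written, that person counts as free of it and may fall into too low a CMMS category.

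An absent code reads as no disease, not as a missing value, so the 10% missing-data rules in section 9.7.1 do not apply. Exact matching and love plots use the same truncated record and would look balanced. None of the sensitivity analyses in section 9.7.3 varies the look-back.

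Whether a condition is re-coded within a year plausibly depends on contact with care, and section 9.1 says of the control arm that "those who do not engage much with the health system may also be included". The error may therefore differ by arm. At stake are the overall VE and the comorbidity-specific VE, which would be computed in misclassified groups. With the numbers of people described in section 9.5, confidence intervals are likely to be narrow and will not reflect this error.

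**Working it through.** The protocol has no figure to reproduce here: it gives no recording rate, comorbidity prevalence or comorbidity rate ratio. All values below are assumptions, shown as ranges.

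**Model.** There is one binary comorbidity with true prevalence p and outcome rate ratio R. A share s of true cases is coded within the window, and there are no false codes. Controls are matched to vaccinated people on the recorded status. Subscripts v and u denote vaccinated people and controls.

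- Hidden comorbidity among people recorded as free of it: q = p(1 − s)/(1 − p·s)
- Share of the matched cohort with a recorded comorbidity: w = p_v·s_v
- Bias factor in the stratum with none recorded: [1 + (R − 1)q_v]/[1 + (R − 1)q_u]
- Pooled bias factor: B = {wR + (1 − w)[1 + (R − 1)q_v]}/{wR + (1 − w)[1 + (R − 1)q_u]}
- Apparent VE = 1 − (1 − true VE)·B

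**Equal prevalence, poorer recording in controls** (p = 0.3, R = 3, s = 0.8 against 0.6).

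- q_v = 0.06/0.76 = 7.9%; q_u = 0.12/0.82 = 14.6%
- None-recorded stratum: 1.158/1.293 = 0.896, so an ineffective vaccine shows VE of about 10% in that stratum
- Pooled, with w = 0.24: 1.600/1.702 = 0.940, so the spurious VE is about 6%, and a true VE of 60% shows as 1 − 0.4 × 0.940 = 62.4%

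**Upper end of the equal-prevalence range** (p = 0.4, R = 5, s = 0.9 against 0.6).

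- q_v = 0.04/0.64 = 6.25%; q_u = 0.16/0.76 = 21.1%
- None-recorded stratum: 1.25/1.842 = 0.679, a spurious VE of about 32%
- Pooled, with w = 0.36: 2.60/2.98 = 0.873, a spurious VE of about 13%

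**Pooled apparent VE when the true VE is 80%, letting prevalence differ by arm.**

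| Prevalence, vaccinated / controls | Capture, vaccinated / controls | R = 2 | R = 3 | R = 5 |
|---|---|---|---|---|
| 30% / 30% | 90% / 60% | 81.1% | 81.8% | 82.5% |
| 30% / 30% | 90% / 80% | 80.4% | 80.7% | 81.0% |
| 30% / 30% | 60% / 60% | 80.0% | 80.0% | 80.0% |
| 40% / 20% | 80% / 80% | 79.3% | 78.9% | 78.4% |
| 40% / 20% | 60% / 60% | 78.6% | 77.8% | 76.7% |
| 40% / 20% | 90% / 60% | 80.3% | 80.4% | 80.5% |
| 40% / 20% | 80% / 60% | 79.7% | 79.6% | 79.4% |

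In these scenarios, poorer recording in controls alone pushes VE up, sicker vaccinated people alone push it down, and the two together largely cancel. Over the same scenarios, the bias runs from −6.5 to +4.9 points at a true VE of 60%, and from −1.6 to +1.2 points at 90%. With complete capture (s = 1 in both arms), q_v = q_u = 0 and the bias disappears in this model.

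**The case against.** A reader might infer that the short window inflates VE. The documents do not support that. Section 9.1 expects some controls with little contact with care, but it also expects controls receiving terminal care, who may be well coded. It adds that people aged 16 to 64 with comorbidities were recommended for early vaccination. Section 9.5 agrees with this: 79% of at-risk people aged 16 to 64 were vaccinated, against 42.1% of the cohort. Sicker vaccinated people with similar recording in both arms would bias VE downward. This objection stands, and the sign is open.

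A reader might also take the 10% or 32% as the effect on the main estimate. Those figures apply only to the stratum with no recorded comorbidity. The pooled counterparts are about 6% and 13%, for an ineffective vaccine.

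The model is also simpler than the design. Matching on general practice, where used, may balance coding habits in part, and adjustment for prescribed medications and frailty score may recover some information. The true bias could therefore be smaller than shown.

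BMI and smoking are in a different position. A value not measured within the window is missing and goes to complete-case analysis or additional multiple imputation. Only if obesity or smoking were read from codes alone could it default to no.

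Finally, Table 6 gives no length for the baseline period, section 9.2.2 sets only a minimum, and the SAP may refine definitions. A longer look-back may be what is intended. But section 9.7.1 states 12 months in plain terms, so the wording needs correcting even then. Where the plan wants full history it says so: section 9.2.2 takes prior infection from the start of the testing datasets. The validation in section 9.4 compares prevalence between data sources and would not reveal a window that both share.

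**Conclusion.** The point holds as misclassification of long-standing comorbidity in the main matching variable, with residual confounding that is avoidable and of uncertain sign. The rule is stated in the protocol, so this is not a detail left to the SAP.

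Under assumed capture rates and equal true prevalence, an ineffective vaccine shows a pooled spurious VE of about 6% in the central scenario and about 13% at the upper end. At a true VE of 80%, the pooled estimate lies between about 77% and 82.5% once prevalence may differ by arm. The pooled effect is modest. Within comorbidity strata it can be larger, because those groups are themselves misclassified. That the 12-month rule can miss older codes follows from the text. How often it does, and in which arm more often, is not known from the document.

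**What to change.** In section 9.7.1 and Table 6, identify chronic conditions, and so the CMMS and the JCVI comorbidity flags, from all available record history up to the day before index. Take the latest recorded BMI and smoking status on the same basis, which also reduces missingness. Keep 12 months as the minimum coverage requirement in section 9.2.2 and as the window for time-limited items such as current prescriptions.

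The cost is a wording change in two places and a wider extraction window on the same records. The small downside is that history length varies between people. That can be checked by length of registration, or by a sensitivity analysis that keeps the 12-month window.

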9.5 Study Size

The NHS Digital database comprises data from the national registries of vaccination and hospitalization with linkage to the CMR, lab, and mortality data. It is the largest dataset possible for England and covers all regions. As of early March 2021, near 20 million people in England have been vaccinated with at least 1 dose of any COVID-19 vaccines. According to a recent study in Scotland (Vasileiou et al 2021), the Oxford/AstraZeneca vaccine have been used by the majority of the 75+ years old age group and by a significant proportion of the 60-65- and 70-75-years old age groups.

Based on the preliminary count of the cohort of VE from ORCHID in collaboration with PHE (N=5.4 million), as of 7/4/2021, 42.1% of the population have received a COVID-19 vaccine. Overall, 91% of people 80 years and older, 91% of people 65-79 years old, and 79% of people aged 16-64 years old in risk groups were vaccinated. Of those vaccinated, 38% has received the Oxford/AstraZeneca COVID-19 vaccine, i.e. more than 7 million people. It is expected that almost all of England's COVID-19 vaccination data are included in the NHS Digital databases representing the best option for this type of study. Given a large number of people vaccinated with the Oxford/AstraZeneca COVID-19 vaccine and the use of the national database, the study should have sufficient power to address the study objectives.

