Adjusted estimates of cumulative healthcare utilisation counts, lengths of stay and costs, and between-group difference in counts, length of stay and costs, will be obtained from the regressions by summing interval-specific estimates over the time period of interest, a strategy originally reported by Lin (2000). Standard errors and confidence intervals around the mean estimates will be obtained via the robust variance/sandwich estimator, which provides a degree of robustness to departures from normality of errors and misspecification of the GEE working correlation matrix. An alternative approach for estimating standard errors and 95% confidence intervals is through the use of non-parametric bootstrapping. This would involve randomly sampling individual patients with replacement from the data to generate, for example, 1000 replicate datasets, and then fitting regression models to each replicate dataset and calculating adjusted bootstrap estimates of cumulative counts, lengths of stay and costs and the respective between-group differences. However, we recognise that the non-parametric bootstrap method can be computationally expensive for large sample applications such as ours. As a sensitivity check of the results generated by our primary modelling approach, we will therefore also apply the nonparametric bootstrap method to a smaller sample of data to obtain bias-corrected standard errors and confidence intervals. For completeness, the analyses will be repeated by restricting to patients with complete data over 1, 3 and 6 months of follow-up. The approaches to handling potential confounding will mirror those adopted by the statistical analyses. The analyses will also be repeated by the subgroups pre-specified by the statistical analyses.

We will also report the health care resource use and health care costs by COVID-19 risk group, using the JCVI risk group classification.

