9.11 Bias

9.11.1 Methods to Minimize Bias

The advantages of having a control group is that it provides a direct comparison with less impact of potential time-varying rate of events. The disadvantages are that there may be potential differences between people who chose to vaccinate vs not. Also, few concurrent control people in the older age group may be available leading to different age composition of the study arms. This means the concurrent control arm may have more younger people which is expected to have lower hospitalization/death. For this reason, adjustment for age is critical.

It is expected that rates of outcome events are time-dependent and they are subject to the impact of waves of infection and isolation methods such as the use of masks (which may be less early in the pandemic), travel restrictions, lockdown (by waves of infection). Therefore, studying the historical population in the pre-vaccination periods, when testing was more common and there was increased circulation of infection enables us to contextualize the results and assess the potential impact of different time periods on the analysis.

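### Section 9.7.1 promises a weekly 1:1 match for all vaccinees but gives no rule on reusing controls; if controls are reused, the VE intervals need a person-clustered variance

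*Protocol*

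**What the plan says.** Protocol section 9.7.1 sets the matching rule: "each week starting from 8th December 2020", "we will match all newly vaccinated persons in a 1:1 ratio to unvaccinated controls". Exact matching is subject to feasibility. Under section 9.2.2 the control pool is "People who have not (yet) received any COVID-19 vaccine", so it includes people who are vaccinated later. A control who is vaccinated is censored and may return as a vaccinee (9.2.1, 9.7.1), and the vaccinated partner is censored at the same time (9.2.4). Nothing is said on whether one unvaccinated person may be control for more than one vaccinee.

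The VE model in 9.7.1 is stated as: "Poisson regression with offset for time at risk will be used to estimate rates using the matched dataset, adjusting for the matching variables and BMI" and further covariates. The section promises 95% CIs and two-sided 5% tests but names no variance estimator. For the cost analysis, section 9.7.6.2 says that standard errors "will be obtained via the robust variance/sandwich estimator".

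Section 9.5 gives coverage at 7 April 2021: "Overall, 91% of people 80 years and older, 91% of people 65-79 years old", 79% in risk groups aged 16-64, and 42.1% of the whole cohort. Section 9.11.1 concedes that "few concurrent control people in the older age group may be available".

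**The concern.** Where nine in ten people are vaccinated, few remain to act as controls, and the plan wants one for every vaccinee. Either some vaccinees go unmatched, or the same unvaccinated people are drawn again in later weeks. The protocol does not choose.

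The choice matters for precision. If a person is control in three pairs at once and is then hospitalized, the matched dataset holds three control events from one admission. A Poisson model with its default variance counts them as three independent events, so the interval for VE is too narrow. This bites most in the older and comorbid groups that the primary objective singles out, and where RR is near 1, as may happen for early post-dose periods or all-cause outcomes. If controls are not reused, the intervals are unaffected, but a sizeable share of older vaccinees drops out and the promise to match all of them is not kept.

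**Working it through.** **The plan's own figures.** The protocol gives no expected events, power, SE or CI width for VE, so there is none to reproduce. Its one size figure checks: about 20 million x 38% = 7.6 million, consistent with more than 7 million.

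**Step 1: can everyone be matched without reuse?** Inputs are coverage v = 0.91, 0.79 and 0.421 (section 9.5). From 8 December 2020 to 7 April 2021 is 17.1 weeks.
- In principle, matching without reuse works only if no week vaccinates more than the never-vaccinated share of the stratum. At 91% that limit is 9% per week, against mean uptake of 91/17.1 = 5.3%. Even uptake passes. The same check on section 9.1 (over 90% at ages 70+ by 22 March 2021, about 14.9 weeks) gives 6.1% per week against 10%, so a peak week of about 1.65 times the mean breaks it.
- With random draws the answer is different. Let w be the share of the stratum that is unvaccinated and not yet used as a control. Then dw/dv = -w/(1-v) - 1 with w(0) = 1, so w = (1-v)(1 + ln(1-v)). This is zero at v = 1 - 1/e = 0.632.
- Unmatched share: 1 - 0.632/0.91 = 31% and 1 - 0.632/0.79 = 20%. Simulated weekly draws with even uptake give about 32% and 22%. Peaked or front-loaded uptake gives 35-37% and 24-26%. At 42.1% as a single stratum, all vaccinees are matched.

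**Step 2: how much reuse would matching everyone imply?** With reuse, a never-vaccinated person is drawn on average -ln(1 - 0.91) = 2.4 times. In simulation at 91% coverage, controls were used 1.8-1.95 times on average and about half were used more than once.

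**Step 3: effect on the standard error if controls are reused.** Let m be a control's concurrent rows and D = sum(m^2)/sum(m). The naive variance of log RR is proportional to 1/(1-VE) + 1, and the true one to 1/(1-VE) + D, so the SE ratio is the square root of [1/(1-VE) + D] / [1/(1-VE) + 1]. At 91% coverage, D was 2.5 to 3.3 over three assumed uptake curves and a 30-week horizon:
- RR = 1: sqrt(3.5/2) = 1.32 to sqrt(4.26/2) = 1.46.
- VE 50%: sqrt(4.5/3) = 1.22 to sqrt(5.26/3) = 1.32; CI coverage 86-89%.
- VE 80%: sqrt(7.5/6) = 1.12 to sqrt(8.26/6) = 1.17; CI coverage 91-92%.
- VE 90%: sqrt(12.5/11) = 1.07 to sqrt(13.26/11) = 1.10; CI coverage about 93%.

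At 42.1% coverage the ratio is 1.02-1.09 for VE from 90% down to 50% (CI coverage 93-94.5%).

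**Step 4: direct simulation.** Assumed: one stratum of 20,000 people, 17 weeks of uptake, constant hazard, 40 weeks of follow-up, pair censoring as in section 9.2.4. At 91% coverage:
- In one set of runs 82 counted control events came from 42 people; in another, 123 came from 62.
- At RR = 1 the true SD was about 1.35-1.4 times the naive SE, and the false-positive rate about 14-15% instead of 5% (about 11% with 17 weeks of follow-up).
- At VE 50% the ratio was about 1.25-1.3, with CI coverage of about 86-88%.
- At VE 80% the ratio was about 1.16, with CI coverage of about 89-93%.
- A person-clustered sandwich variance restored coverage to about 93-96%. The point estimate was unbiased throughout.

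**The case against.** The strongest reply is that two silences are being read as an error. Reuse of a control for several vaccinees is stated nowhere. The only reuse the protocol grants is from control to later vaccinee, and those periods do not overlap. The synopsis makes weekly matching itself subject to feasibility, 9.7.1 does the same for exact matching, and 9.11.1 expects few older controls, so incomplete matching is arguably foreseen. The variance estimator is ordinarily left to the SAP, which is announced and not shown. A sandwich variance is routine for GEE, so naming it for costs does not show that it was rejected for VE.

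Most of this stands. A reader might infer that the plan forces reuse and that the primary 95% CIs are therefore too narrow. The document supports neither as fact: even uptake stays below the 9% limit, random selection is an assumption, and no variance estimator is named. The 91% applies to ages 65 and over only, and the effect is modest if VE is 80-90%.

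What does not fall is the mismatch inside the protocol. Section 9.7.1 says all vaccinees are matched. Reaching that without reuse at 91% coverage would need almost every future vaccinee to serve as a control once before vaccination, which random weekly draws do not deliver. The feasibility wording does not say that vaccinees may be dropped, and no reporting of such a loss is planned.

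**Conclusion.** The point holds as a conditional one. At the protocol's own coverage for older people and risk groups, matching every vaccinee and never reusing a control are not compatible in practice, and the protocol does not say which gives way.

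If controls are reused, a model-based Poisson variance understates the SE of log RR by a factor of about 1.16 (VE 80%) to 1.4 (RR = 1) in strata at 91% coverage. If they are not, about 32% of vaccinees in those strata and 22% in the risk groups aged 16-64 go unmatched. The effect on precision is small for the pooled cohort at 42.1% (a figure that treats the cohort as one stratum and ignores age matching) and at very high VE, and there is no bias in VE from this source. The sizes rest on assumed uptake curves, random choice of controls, a constant hazard and the 40-week follow-up, none of which the protocol gives.

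**What to change.** In section 9.7.1:
- State whether controls are drawn with or without replacement across weeks.
- Compute all VE 95% CIs and p-values with a sandwich variance clustered on the unique person, or with a bootstrap that resamples persons. All rows of one person, as repeated control and as later vaccinee, form one cluster. This corrects the intervals under reuse and leaves them essentially unchanged without it.
- Report the number of unique controls and unique control events beside the matched counts.
- If matching is without replacement, replace the promise to match all vaccinees and report the unmatched share by age band and risk group.

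The cost is a few sentences and a standard option in R, with no new data. The downside is somewhat wider intervals in high-coverage strata.
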